#### *Statistical Methods*

To assess our primary outcome (the difference in basal SNA between groups) a 2 way mixed model (group x time) ANOVA will be used. To assess the influence of exercise on our secondary outcomes (i.e. vascular function and blood markers) a similar 2 way mixed model design will be used. Tukey's post hoc analysis will be used to compare means when main effects are found to be significant.

The strength of the association between changes in SNA, vascular measures and blood markers within and across groups will be determined using the Pearson product-moment correlation coefficient. Statistical analyses will be performed using SPSS Version 16.0 (SPSS, Chicago, IL). Statistical significance will be assumed at  $P < 0.05$ .

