### 2.2. Hypotheses

- 1) *We hypothesize that exercise training will blunt the increase in SNA which occurs with pregnancy.*
- 2) *We hypothesize that vascular reactivity to sympathetic stressors will be reduced in women who are taking part in a structured exercise program compared to those that have not.*

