After instrumentation (described below) and an initial period of 20 min of rest, participants will undergo baseline testing which consists of arterial stiffness (pulse-wave velocity and ultrasound) and carotid distensibility. Next, participants will undergo 3 separate conditions separated by 20 minutes of quiet rest: **1)** 3 min with their hand in an ice bath (cold pressor test); **2)** Flow mediated dilation (~15 minutes) and **3)** an end expiratory breath hold (~15s). Following the cold pressor test a heating pad will be used to warm the hand to baseline temperature.

**Postpartum Visit)** Participants will arrive after refraining from exercise, caffeine, alcohol or food for 12 h (overnight fast) and blood samples will be collected. Following the blood draw, anthropometrics will be recorded and a standardized breakfast will be provided. Participants will then undergo an assessment of blood vessel health. After instrumentation (described below, but without microneurography), participants will undergo testing which consists of arterial stiffness (pulse-wave velocity and ultrasound) and carotid distensibility. Following this, participants will undergo an assessment of flow mediated dilation (described above).

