### 3.2 Subject Selection and Withdrawal

One hundred pregnant women (>18yrs, with singleton pregnancies) will be recruited between 16-20 weeks gestation through physician and midwife referrals, newspaper advertisements and recruitment posters. Women diagnosed with multiple pregnancies will be excluded. Eligible women will be randomized to take part in an exercise intervention (n=50) or no intervention (n=50). The intervention will consist of aerobic exercise equivalent to 50-70% of heart rate reserve, 3-4 times per week until the end of the study (34-36 weeks). For initial baseline testing (16-20 weeks) and at the end of the intervention (34-36 weeks), participants will visit the laboratory twice. Following initial baseline testing, women will be randomly assigned to an exercise intervention or no intervention. Women will receive an opaque sequentially numbered envelop with their allocation. Allocation will be determined using a randomly generated allocation sequence by an individual not associated with the research study who will place and seal the allocation in the envelope.

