### **3.4 Statistical Plan**

#### *Sample Size Determination*

Our primary hypothesis is that exercise training will reduce resting SNA (burst/min) in pregnant women. Data from other clinical populations with high resting SNA indicates a ~23% decrease in resting SNA with exercise training (4). Previous data collected in our lab demonstrate a resting burst frequency of  $40 \pm 11$  burst/min. Based on previous findings we expect exercise training to reduce resting SNA to  $\sim 31 \pm 11$  bursts/min (-23%). Using these data we estimate 22 pregnant women are required to observe a significant reduction in SNA following exercise training (80% power,  $\alpha = 0.05$ ; G\*Power v3.16 (10)). We expect an 80% success rate for obtaining an appropriate SNA signal and an 80% retention rate, requiring 43 women to be recruited into the

training arm of the study. To allow for additional variability and or decreased retention we will recruit 50 pregnant women to take part in exercise training and 50 pregnant women to take part as controls.

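### The group x time ANOVA compares SNA changes without adjusting for baseline; adjustment would cut the variance by about 25% at an assumed correlation of 0.5, on complete pairs or on all recordings

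*Combined protocol and SAP*

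**What the plan says.** Statistical Methods (section 3.4) introduces the primary analysis with "To assess our primary outcome (the difference in basal SNA between groups" and then states that "a 2 way mixed model (group x time) ANOVA will be used". It names no baseline covariate, does not constrain the baseline means, and defines no analysis set. It does not say which term of the ANOVA decides the question. Tukey's "post hoc analysis will be used to compare means when main effects are found to be significant", which points to main effects rather than the interaction.

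Three other places fix the structure of the data:

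- Section 3.1, General Design, sets testing at 16-20 weeks, 34-36 weeks and two months postpartum. The postpartum visit proceeds "After instrumentation (described below, but without microneurography", so SNA has two time points only.
- Section 3.2 states: "Following initial baseline testing, women will be randomly assigned to an exercise intervention or no intervention". The first SNA recording is therefore a true pre-randomisation baseline.
- Hypothesis 1 in section 2.2 reads: "We hypothesize that exercise training will blunt the increase in SNA which occurs with pregnancy". This is a statement about change, and it supports reading the interaction as the primary test.

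Sample Size Determination (section 3.4) allows for losses as follows: "We expect an 80% success rate for obtaining an appropriate SNA signal and an 80% retention rate, requiring 43 women".

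**The concern.** With two time points, the group x time interaction is the difference between arms in mean change. Because randomisation follows the baseline recording, both arms have the same expected baseline mean, and any observed baseline difference is chance. Subtracting the whole baseline value, as a change score does, is not the most precise way to remove that chance difference. Regressing on baseline, or fitting one common baseline mean, does better whenever r is below 1 and the SDs are equal.

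Precision is at stake, not bias. Usable recordings are scarce in this trial: the plan's own allowances leave about half of the randomised women with a usable pair. No value of r is given, so the power of the unadjusted contrast is unknown. If r is low, it could fall below the 80% target even with 50 women per arm.

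**Working it through.** **The plan's own figures.** For a difference of 9 (40 to 31 bursts/min), SD 11, two-sided alpha 0.05 and 80% power, the two-sample normal formula gives 2 × (1.96 + 0.842)² × 121 / 81 = 23.5, so 24 per arm. With 9.2 (exactly 23% of 40) it gives 23. These are close to the stated 22. A paired t-test gives exactly 22 at r of about 0.15. The inflated figure is 22 / 0.8³ = 42.97, so 43, whereas 22 / 0.8² = 34.4 does not reproduce it. The plan therefore appears to count signal success at both visits, which suggests complete pairs.

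**Inputs.** From the documents: 50 per arm, SD 11, 80% retention, 80% signal success. Assumed: the SD applies at both visits; 9 bursts/min is the between-group difference (the plan gives it as a fall with training); signal success is independent between visits; r = 0.3, 0.5 or 0.7.

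**Expected recordings per 50 randomised**
- both visits: 50 × 0.8 × 0.8² = 25.6
- follow-up only: 50 × 0.8 × 0.8 × 0.2 = 6.4
- baseline only: 50 × 0.8 − 25.6 = 14.4
- neither: 3.6

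**Reading A, complete pairs.**
- Unadjusted change: variance = (2/25.6) × 2 × 121 × (1 − r)
- Baseline-adjusted: variance = (2/25.6) × 121 × (1 − r²)
- Ratio = (1 + r)/2, so the reduction is (1 − r)/2

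At r = 0.5 these are 9.45 and 7.09, a reduction of 25%.

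**Reading B, all valid recordings.** These are generalised least squares variances with covariance 121 × [[1, r], [r, 1]]. Per arm, the information for the two visit means has:
- I₀₀ = 25.6/(121(1 − r²)) + 14.4/121
- I₁₁ = 25.6/(121(1 − r²)) + 6.4/121
- I₀₁ = −25.6r/(121(1 − r²))

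With free baseline means, invert this matrix to V; the interaction variance is 2(V₀₀ + V₁₁ − 2V₀₁). With a common baseline mean, the variance of the follow-up difference is 2/I₁₁. At r = 0.5, I₁₁ = 0.2821 + 0.0529 = 0.3350, giving 5.97 against 7.93.

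**Results.** Power is Φ(9/SE − 1.96); each cell gives r = 0.3 / 0.5 / 0.7.

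| | Variance | SE | Power (%) |
|---|---|---|---|
| A, planned | 13.23 / 9.45 / 5.67 | 3.64 / 3.07 / 2.38 | 70 / 83 / 97 |
| A, adjusted | 8.60 / 7.09 / 4.82 | 2.93 / 2.66 / 2.20 | 87 / 92 / 98 |
| B, planned | 10.42 / 7.93 / 5.09 | 3.23 / 2.82 / 2.26 | 80 / 89 / 98 |
| B, common baseline | 7.01 / 5.97 / 4.28 | 2.65 / 2.44 / 2.07 | 93 / 96 / 99 |

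The variance falls by 35/25/15% on A and 33/25/16% on B. Extra women per arm for the same gain, 50 × (variance ratio − 1), are 26.9/16.7/8.8 on A and 24.4/16.4/9.5 on B. At r = 0.8 the variance falls from 3.78 to 3.40 on A (10%) and from 3.51 to 3.12 on B (11%), with planned power already above 99%.

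**Robustness.**
- Simulation of 4,000 trials per r with t reference distributions gives slightly lower power: A 67/82/96% rising to 83/90/97%, B 77/88/97% rising to 91/95/99%.
- A separate simulation at r = 0.5, with the slope estimated in small samples, puts the variance reduction at 22% on pairs and 24% on all recordings.
- If signal success has within-woman correlation 0/0.5/1, the reduction at r = 0.5 is 25% throughout on A and 25/23/21% on B.

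**If the group main effect were the test instead** (complete pairs): the expected difference averages in the pre-randomisation visit, (0 + 9)/2 = 4.5, with variance 121(1 + r)/25.6. Power is then 44/39/35%. Taking the interaction as the test is thus the reading kinder to the plan.

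**The case against.** The strongest reply is that nothing here is an error. Under randomisation the comparison of changes is unbiased, the expected 25.6 pairs per arm exceed the 22 required, and at r = 0.5 or 0.7 planned power is above 80% on both readings. That is correct: the point concerns efficiency only.

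The 25% also depends on equal SDs at the two visits as well as on r. The plan gives 11 twice, but the second figure is an expectation for trained women; none is given for controls late in pregnancy. With baseline SD s₁ and follow-up SD s₂, the complete-pair reduction is (s₁ − r·s₂)² / (s₁² + s₂² − 2r·s₁·s₂). At s₁ = 11 and r = 0.5 it is 14% for s₂ = 13, 10% for s₂ = 14 and 41% for s₂ = 9; at r = 0.7 and s₂ = 13 it is 4%. So the size is uncertain, but the expression is a square over a variance and cannot be negative. Adjustment never loses like for like, apart from the small cost of estimating the slope.

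The form of adjustment matters too. Ordinary ANCOVA on complete pairs, set against a mixed model that already uses all recordings, gains only 17/11/5% at r = 0.3/0.5/0.7. The full gain on reading B needs the common-baseline model.

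Finally, the plan does not name the interaction as the test. That assumption stands as an assumption, and the main-effect alternative would serve the trial worse.

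**Conclusion.** The concern holds. If the interaction is the primary test, the plan compares unadjusted changes and forgoes precision that its own baseline recording would supply. The variance reduction is about 25% at r = 0.5 on either analysis set, and runs from 33-35% at r = 0.3 to 10-11% at r = 0.8. It rests on an assumed r, an SD of 11 at both visits and, for the power figures only, 9 bursts/min as the between-group difference. The gain matters most where the plan is most exposed: at r = 0.3, complete-pair power is 70% unadjusted and 87% adjusted.

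A lesser point applies to complete pairs only and is an inference. Women with a valid 34-36 week recording but no valid baseline would be dropped: 12.8/6.4/0% of those randomised at signal correlations of 0/0.5/1. This supposes that women with a failed baseline recording are still randomised and recorded again, which section 3.2 neither requires nor rules out.

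**What to change.** In Statistical Methods (section 3.4), define the primary estimate as the group difference in burst frequency at 34-36 weeks, adjusted for baseline, with a 95% confidence interval. Analyse women by allocated arm, including all randomised women with at least one valid SNA recording. Fit a REML mixed model with unstructured covariance and a common baseline mean. ANCOVA on complete pairs is an acceptable simpler form, and secures most of the gain over a complete-pair ANOVA. Keep complete pairs as a sensitivity analysis. Report by arm how many women have both recordings, baseline only, follow-up only and neither.

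This costs some SAP wording and slightly more analysis work, with no extra women or visits. The all-recordings model assumes outcomes are missing at random. The change does not remove the trial's dependence on retention and on signal success at follow-up.

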## 2 STUDY OBJECTIVES

### 2.1. Specific Aims

- 1) *Determine the role of exercise in regulating sympathetic activity during pregnancy.*
- 2) *Determine the impact of exercise on vascular reactivity and function during pregnancy.*

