## 3 PATIENTS AND METHODS

### 3.1 Study Design

#### *General Design*

BASELINE (16-20 weeks), POST-INTERVENTION (34-36 weeks), AND POSTPARTUM (2 months): At each time-point during pregnancy, participants will report to the laboratory on two occasions. Women will report to the laboratory once in the postpartum.

**Visit 1)** Participants will complete a peak exercise test on the treadmill or bike to volitional fatigue. Instrumentation will include breathing through a mouthpiece attached to a metabolic cart (measures how and what the participant is breathing), heart rate, blood pressure and transcranial doppler ultrasound (TCD) to measure blood flow in the brain (middle cerebral artery). Resting diameter and flow of the internal carotid artery (ICA) will be assessed at rest. Lung capacity will be assessed at rest using spirometry. Participants will then warm up for 5 minutes at 3.4mph and 0% grade. After the warm up, the incline will increase in 1% increments until volitional fatigue. The test will be followed by a 5 minute cool down. Participants will hold the hand-rails through-out the peak test (5; 7). Exercise on the bike will follow a similar protocol of 5 minutes of rest, 5 minutes of warm-up at 0.5kpa. Exercise intensity will increase by 0.5kpa until volitional fatigue, followed by a 5 minutes of cool down and 5 minutes of rest.

**Visit 2)** Participants will arrive after refraining from exercise, caffeine, alcohol or food for 12 h (overnight fast) and blood samples will be collected. Following centrifugation, aliquots will be frozen at -80°C until analysis. A finger poke will be used to measure glucose via glucometer and blood gases and metabolites (blood gas analyzer). Following the blood draw, anthropometrics will be recorded and a standardized breakfast will be provided. Participants will then undergo an assessment of reflex neurovascular control. Participants will rest in a dentist chair 30° above supine for the duration of testing to minimize discomfort of the pregnant women.

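### For outcomes repeated at 2 months postpartum, the plan states neither the levels of time nor the contrast that tests exercise; if postpartum enters the ANOVA, no stated test isolates the 34-36 week effect.

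*Combined protocol and SAP*

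**What the plan says.** General Design (section 3.1) sets three laboratory time points: "BASELINE (16-20 weeks), POST-INTERVENTION (34-36 weeks), AND POSTPARTUM (2 months"). At the postpartum visit blood is drawn, instrumentation is "described below, but without microneurography", and "participants will undergo testing which consists of arterial stiffness (pulse-wave velocity and ultrasound) and carotid distensibility". Flow-mediated dilation comes last: "Following this, participants will undergo an assessment of flow mediated dilation (described above").

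Section 3.2 places the end of training at 34-36 weeks: "3-4 times per week until the end of the study (34-36 weeks"). Aim 2 in section 2.1 is to "Determine the impact of exercise on vascular reactivity and function during pregnancy".

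Statistical Methods (section 3.4) gives the primary outcome a group x time mixed ANOVA and says of the secondary outcomes that "a similar 2 way mixed model design will be used". It then adds: "Tukey's post hoc analysis will be used to compare means when main effects are found to be significant". It gives no list of time levels, names no term as the test of exercise, and mentions neither a 34-36 week contrast nor a separate postpartum analysis.

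**The concern.** Aim 2 asks about pregnancy, and training stops at 34-36 weeks. With three visits in the time factor, the ANOVA offers two terms that involve group. The interaction (2 df) asks whether the group difference varies in any way across the three visits. The group main effect averages the group difference over a visit before randomisation, the target visit, and a visit after training has ended. Neither is the group difference at 34-36 weeks.

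Two things are at stake. A significant interaction could be reported as a vascular benefit in pregnancy when the groups differ only postpartum. And the plan gives no clear way to locate an effect, because its follow-up comparisons depend on main effects and the interaction is not mentioned.

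**Working it through.** **The plan's own figure.** The only sample-size figure is 22 women, for sympathetic nerve activity. A two-sided normal approximation with a difference of 9 and an SD of 11 gives 2 x (1.96 + 0.842)² x (11/9)² = 23.5, so 24 per arm; a difference of 9.2 (23% of 40) gives 23. That is close to 22. No power is stated for any outcome repeated postpartum, so the plan has no figure to reproduce for this point.

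**Inputs.** From the documents: 50 per arm (section 3.2), 80% retention and alpha 0.05 (section 3.4). This gives n = 50 x 0.8 = 40 per arm for outcomes that need no nerve signal. Assumed, not in the documents: two-sided testing, equal variances, the same correlation r between any two visits (0.5, with 0.3 and 0.7 as a range), and the effect sizes below. Effects δ are in SD units at (16-20 weeks, 34-36 weeks, postpartum).

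**Formulas.**
- Interaction with K visits: λ = (n/2) Σ(δₖ − δ̄)² / (1 − r), noncentral F on K−1 and (K−1)(2n−2) df.
- Group main effect: noncentrality δ̄ √(n/2) / √[(1 + (K−1)r)/K], t on 78 df.
- Baseline-adjusted 34-36 week contrast: noncentrality δ √[(n/2)/(1 − r²)], t on 77 df.

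**Step 1: a difference only postpartum, r = 0.5.**
- δ = (0, 0, 0.6): Σ(δₖ − δ̄)² = 0.04 + 0.04 + 0.16 = 0.24; λ = 20 x 0.24 / 0.5 = 9.6 on 2 and 156 df; significant in 79%.
- δ = (0, 0, 0.3): the sum is 0.06, λ = 2.4; significant in 26%.
- The 34-36 week contrast is significant in 5% in both cases, since the effect there is zero.
- For 0.6 SD, the interaction figure is 64% at r = 0.3 and 95% at r = 0.7.

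**Step 2: a true 0.5 SD effect at 34-36 weeks, r = 0.5.**

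| Test | None persists | Half persists | All persists |
|---|---|---|---|
| Interaction, 3 visits | 62% (λ = 6.67) | 50% (λ = 5.0) | 62% (λ = 6.67) |
| Group main effect, 3 visits | 15% | 27% | 44% |
| Interaction, 2 visits (change from baseline) | 60% (λ = 5.0) | 60% | 60% |
| Group main effect, 2 visits | 25% | 25% | 25% |
| Baseline-adjusted contrast at 34-36 weeks | 72% | 72% | 72% |

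The last row: 0.5 x √(20/0.75) = 2.58, power 72%. With half persistence the 3-visit λ equals the 2-visit λ but is spread over 2 df, which is why power drops there.

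**Step 3: other correlations, same 0.5 SD effect.** Order: 2-visit interaction; 3-visit interaction (none / half / all persists); adjusted contrast.
- r = 0.3: 46%; 48 / 37 / 48%; 64%.
- r = 0.7: 81%; 85 / 73 / 85%; 87%.

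The adjusted contrast also exceeds the 3-visit group main effect in all of these settings; the highest main-effect figure is 52%, at r = 0.3 with full persistence.

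Simulation of the r = 0.5 cases agrees within about 2 percentage points: 59% for the 2-visit test; 61 / 49 / 61% for the 3-visit interaction; 80% for the 0.6 SD postpartum-only case.

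**The case against.** **Three levels of time is an inference.** Statistical Methods never says that postpartum data enter the model. The secondary model is described by likeness to the primary one, which can have only two levels because there is no microneurography postpartum. Section 3.2 also calls 34-36 weeks the end of the study. This stands, and the point is therefore conditional. It does not remove the gap: if two levels are meant, the plan should say so, and the postpartum measurements then have no stated analysis.

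**A reader might infer that the third visit dilutes the pregnancy effect.** That is not generally so. Against the like-for-like 2-visit interaction, the 3-visit interaction gains about 2 points with no or full persistence and loses about 10 with half. The group main effect is weak with two visits as well, because it averages over a pre-randomisation baseline. Most of the advantage of the recommended contrast comes from baseline adjustment: 60% to 72%.

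**A reader might infer that all of Aim 2 is affected.** The cold pressor response and cerebrovascular reactivity to exercise, which bear on Hypothesis 2, are not listed at the postpartum visit. Flow-mediated dilation is tertiary, carotid distensibility is not named in the outcome lists, and the assays to be run on postpartum blood are not itemised. Resting pulse-wave velocity is the clearest affected secondary outcome.

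**A reader might infer that a missed postpartum visit removes a woman from the 34-36 week comparison.** The plan states no missing-data rule, so this depends on the procedure run and cannot be asserted.

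**A postpartum-only difference of 0.6 SD may be unlikely.** The documents give no reason to expect it. It shows what the test can respond to and is not a forecast; at 0.3 SD the figure is still 26%.

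**Tukey comparisons might locate the effect.** They might in part, for instance if the main effect of time is significant. But they are not tied to the interaction, and no pregnancy contrast is named among them.

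**Conclusion.** The point holds in a limited form. For outcomes repeated at 2 months postpartum, the levels of time and the contrast that tests exercise are unspecified. If postpartum is included, a significant omnibus result need not concern pregnancy: with 40 per arm and r = 0.5, the interaction is significant in about 26% (0.3 SD) to 80% (0.6 SD) of trials when the groups differ only postpartum, against 5% for the 34-36 week contrast. These figures rest on the assumed correlation and effect sizes.

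A general loss of power is not supported. What the figures do show is that the baseline-adjusted contrast is more powerful than either 3-visit omnibus term in every persistence pattern examined at r = 0.3, 0.5 and 0.7. The primary outcome is untouched. The change should be made, because it settles what the affected Aim 2 outcomes will be judged on, but it does not threaten the trial's main result.

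**What to change.** In Statistical Methods, for each secondary or tertiary outcome with a postpartum value:

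- State the visits included in the model.
- Make the main test one 1-df comparison of exercise with control at 34-36 weeks, adjusted for the 16-20 week value, by ANCOVA or a likelihood-based mixed model with group x visit.
- Report the group difference at 2 months postpartum as a separately labelled persistence contrast.
- Do not make either comparison conditional on a significant main effect.
- List which blood markers are assayed again postpartum, so that it is clear where this rule applies.

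The cost is SAP wording only; the baseline values are already collected. The small downside is that persistence is tested separately and not within one omnibus test.

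### The plan does not say which term of the group x time ANOVA answers the primary question, and it makes follow-up comparisons depend on main effects that do not isolate the exercise effect

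*Combined protocol and SAP*

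**What the plan says.** Section 3.4, Statistical Methods, is the only account of the inferential analysis. For the primary outcome it states: "To assess our primary outcome (the difference in basal SNA between groups) a 2 way mixed model (group x time) ANOVA will be used". Follow-up is governed by one sentence: "Tukey's post hoc analysis will be used to compare means when main effects are found to be significant". Secondary outcomes get a similar model. The section does not mention an interaction, a baseline-adjusted contrast, or which means Tukey's procedure compares.

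Four other places bear on the reading:

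- Section 2.2 hypothesises that "exercise training will blunt the increase in SNA which occurs with pregnancy".
- Section 3.2 puts randomisation after the baseline visit: "Following initial baseline testing, women will be randomly assigned to an exercise intervention or no intervention".
- Section 3.1 runs the postpartum visit with instrumentation "described below, but without microneurography", so SNA has two time points, 16-20 and 34-36 weeks.
- Sample Size Determination gives its requirement as "22 pregnant women are required to observe a significant reduction in SNA following exercise training", and inflates it for the training arm.

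**The concern.** A blunted rise is a difference between arms in change over time. In a two-arm, two-visit design that is the interaction. Because allocation is random, it can also be estimated as the 34-36 week difference adjusted for baseline. Neither main effect is that quantity:

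- **Group main effect.** It averages the 34-36 week visit with a visit at which exercise cannot yet have acted, so it estimates half the effect.
- **Time main effect.** It pools the change in both arms, so a gestational rise alone can make it significant.

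The text supports at least three primary results: a group main effect, an interaction, or a fall within the training arm. The choice could be made after the data are seen.

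The Tukey sentence adds to this. If it compares the two levels of a main effect, it repeats the F test. If it compares the four group-by-visit cells, the one contrast of interest shares its error rate with five others. Within-arm statements (controls rose, exercisers did not) then become available as apparent support for Hypothesis 1.

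**Working it through.** **Inputs from Sample Size Determination.** Means 40 and 31 bursts/min (difference 9), SD 11, alpha 0.05 (taken as two-sided), 80% power, 50 women per arm, and 80% each for signal success and retention.

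**Assumed.** The within-woman correlation r between visits is not given; results are shown for r = 0.3 / 0.5 / 0.7. The size of the gestational rise is not given either.

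**The plan's own figure.** A two-sample comparison of 9 with SD 11 needs 24 women per arm by the normal approximation and 25 by the exact t test, close to the stated 22. A paired test gives 21 at r = 0.2. The figure therefore does not show which test was intended.

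**Evaluable women.** 50 x 0.8 x 0.8 = 32 per arm. The plan's 43 recruits equals 22/0.8³ (42.97), which would imply 50 x 0.8³ = 25.6, taken as 25. Both are shown.

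**Power of each candidate term.** Noncentral t, with noncentrality = difference / (SD x √(2/n)):

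- Group main effect: difference (0 + 9)/2 = 4.5, SD 11√((1+r)/2), df 2n-2.
- Interaction: difference 9, SD 11√(2(1-r)), df 2n-2.
- Baseline-adjusted ANCOVA: difference 9, SD 11√(1-r²), df 2n-3.

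At n = 32 and r = 0.5, √(2/32) = 0.25. The noncentralities are 4.5/(9.53 x 0.25) = 1.89, 9/(11 x 0.25) = 3.27 and 9/(9.53 x 0.25) = 3.78.

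| Term | 32 per arm, r = 0.3 / 0.5 / 0.7 | 25 per arm, r = 0.3 / 0.5 / 0.7 |
|---|---|---|
| Group main effect | 52 / 46 / 42% | 42 / 37 / 34% |
| Interaction | 78 / 90 / 99% | 67 / 81 / 96% |
| ANCOVA | 92 / 96 / 99.5% | 84 / 91 / 98% |

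**How often the rule blocks follow-up.** Simulation of 40,000 trials per scenario, 32 per arm, bivariate normal. The event is a significant interaction with neither main effect significant.

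| Change, control / exercise | r = 0.3 | r = 0.5 | r = 0.7 |
|---|---|---|---|
| +11 / +2 (both rise) | 0.9% | 0.2% | <0.1% |
| +9 / 0, or 0 / -9 | 8% | 5% | 1% |
| +7 / -2 | 25% | 27% | 21% |
| +4.5 / -4.5 | 36% | 46% | 54% |
| +5 / -9 (difference 14) | 10% | 12% | 12% |

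The +4.5 / -4.5 row is the worst case for a difference of 9. The last row joins the plan's 9-burst fall with an assumed 5-burst rise in controls.

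**How often the rule opens with no exercise effect.** If both arms rise by an assumed 5 bursts/min, the time main effect is significant in 86 / 95 / 99.6% of trials at 32 per arm.

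**Four-cell Tukey reading.** With 62 df, q = 3.734, so the critical t is 3.734/√2 = 2.640 (per-comparison p = 0.0105).

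- Power for the 34-36 week contrast (difference 9, SD 11) falls from 90% to 73%.
- With no exercise effect and a common 5-burst rise, the control change is significant and the exercise change is not in 21 / 24 / 19% of trials. At r = 0.5, about 22 of those 24 points have a non-significant interaction.
- For a common 9-burst rise the pattern appears in 9 / 3 / 0.1%.

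**The case against.** The strongest reply is that a group x time ANOVA conventionally means the interaction is the test. With two arms and two visits it has one degree of freedom, and its direction can be read from the four means. For SNA, a blocked post hoc step then loses little primary inference. This stands in part: the effect is not untested. It does not supply the missing sentence. The wording of the plan points towards a between-group difference and main effects.

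Second, if both arms rise, as Hypothesis 1 suggests, follow-up is almost never blocked (0.2% at r = 0.5). That is correct. The larger rates need the arms to move in opposite directions. That follows only from combining the fall in the sample-size section with the rise in Section 2.2, and the scenario nearest to this gives 12%.

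Third, the group main effect has sound type I error under randomisation. True; the objection to it is half the effect at low power.

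Fourth, the roughly 24% rate of misleading within-arm patterns is not the error rate of a planned test. It depends on the four-cell reading, an assumed 5-burst rise and a reader who treats the pattern as the result. The within-arm reading is itself an inference from the sample-size wording. These caveats stand.

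Finally, 32 evaluable per arm is not stated in the plan. At 25 per arm all powers fall, but their order is unchanged and blocking is more frequent: 12 / 9 / 3% if one arm changes, and 35 / 48 / 61% for +4.5 / -4.5.

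**Conclusion.** The concern holds. The stated follow-up rule is tied to the wrong terms, and the plan leaves open what counts as the primary result. At r = 0.5 the candidate between-arm tests differ in power by a factor of about two (90/46 = 1.96 at 32 per arm). The ratio runs from 1.5 at r = 0.3 to 2.4 at r = 0.7. The ordering group main effect, interaction, ANCOVA holds at every r tried and at both 25 and 32 per arm.

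The cost of the main-effects condition is less certain: negligible if both arms rise, about 5% if one arm moves, and up to about 46% (r = 0.5, 32 per arm) if they diverge equally. The lasting harm is freedom to choose among terms and within-arm comparisons after the fact. This should be fixed, but it does not invalidate the design.

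**What to change.** Replace the main-effects sentence, for the primary outcome, with one named test, for example:

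> The primary test is the exercise-minus-control difference in burst frequency at 34-36 weeks, adjusted for baseline burst frequency (ANCOVA, or the equivalent contrast from a baseline-constrained mixed model), at two-sided alpha 0.05. This single contrast is subject to no main-effect condition and no Tukey adjustment. Within-arm changes are descriptive.

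The minimum repair is to name the group x time interaction as decisive. It would remove nearly all of the false within-arm readings described above. ANCOVA is preferable because it uses the same data with more power: 96% against 90% at r = 0.5 and 32 per arm, or 91% against 81% at 25 per arm.

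Use the same baseline-adjusted contrast for the secondary outcomes, and specify the postpartum comparison as a separate contrast where it is measured.

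The cost is wording only. Baseline SNA is already collected, and no participants or procedures are added.
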